## 6.2 Analysis Methods

*For each primary and secondary outcome, describe what analysis methods will be used and how treatment effects will be presented (e.g. tabular and graphically- Cross-reference to the SAP – Data definitions and Tables). Detail which analysis population will be analysed. Detail any adjustment for covariates. Describe any methods to be used to check statistical assumptions and detail alternative methods if the assumptions do not hold, e.g. normality, proportional hazards. Where multiple analyses are planned, clearly distinguish which analysis will be the principal analysis, on which the outcome of the trial will be assessed, and which will be*

*supporting analyses to aid interpretation. Details of sensitivity analyses and multiple imputation should be detailed either under each key outcome analysis where applicable or in separate sections (5.3 and 5.4)*

The primary endpoint (i.e. the amount of IGF pathway inhibition induced by xentuzumab)s will be presented as in WINGMEN\_DataDefinitions&Tables Section 4.3.1, Figure 1, and Table 6 and analysed as described in Section 4 above.

The trial will be assessed on a modified intention-to-treat basis. Patients who are not evaluable for the primary endpoint may be replaced at the discretion of the Trial Management Group; including:

- Patients who receive fewer than 3 doses of xentuzumab (e.g. due to early withdrawal).
- Patients who for any reason do not have their planned standard of care prostatectomy.
- Patients whose prostatectomy reveals predominantly neuroendocrine/small cell cancer.
- Patients from whom diagnostic biopsy or surgical specimens were not taken or were of insufficient quantity or quality for analysis.
- Patients who do not receive their planned standard of care prostatectomy within 6 days of their final dose of xentuzumab.

All participants who receive one or more doses of xentuzumab will be evaluable for safety analysis, and patients withdrawing early after one or more doses of xentuzumab, irrespective of their stage in the trial, will undergo evaluations on the day before surgery.

The secondary outcomes relate to safety and feasibility of treatment and will be presented as described in Section 4.1.2 and WINGMEN\_DataDefinitions&Tables Section 4.3.2 and Tables 7 and 8. The data will be tabulated and statistical analyses will not be conducted on these results.

In a recent study testing the feasibility of RNA extraction and RNA-seq on FFPE diagnostic prostate biopsies, 19/20 cases were found to provide RNA of sufficient quantity and quality for 3'RNA-seq [7]. The plan to recruit 30 patients to this trial reflects recognition that not all cases may have sufficient tumour tissue in the diagnostic biopsy to provide sections for RNA extraction and research IHC markers. Reasons for unsuitability of research blood and tumour samples are described in the legend to Table 5 in WINGMEN\_DataDefinitions&Tables.

*The completeness of data required for primary and secondary outcomes is described, detailing methods to limit the possibility of missing data and methods for dealing with missing data when it occurs.*

*A description of methods utilised for dealing with missing, spurious (outliers) and unused data during statistical analysis including the assumption for and type of missing data (Missing Completely At Random, Missing At Random, Missing Not At random). If multiple imputation is to be used the methods should be specified, including the imputation method, variables used and number of imputations generated. If multiple Imputation is to be used if appropriate, please clarify what appropriate means, e.g. Multiple imputation will be used if >5% (or >10%) of data is missing, otherwise complete (or available) case analysis will be undertaken. Methods for handling withdrawals and protocol deviations will be documented. State if no missing data adjustment will be used. Where multiple imputation is utilised the methods used to test the validity of the different assumptions will be described, either here or under the sensitivity analyses section.*

### 6.3 Sensitivity Analysis

*Describe any analysis utilised to check the robustness of the results. This may include repeating the primary analysis for different patient populations. Any sensitivity analyses checking the robustness of the results against the missing data assumptions should be included here or in the missing data section.*

Primary endpoint analysis of phospho-IGF-1R and phospho-AKT or S6 IHC will be performed in parallel with controls as in WINGMEN\_DataDefinitions&Tables Figure 1 and will require 2x 4 µm FFPE sections. [name] advises that it is usually possible to cut maximum ~24 4-5 µm sections from a prostate biopsy, so the majority of trial subjects will have additional material if there are technical issues with initial analysis. Method optimisation indicates that IHC is capable of detecting changes in phospho-S6 phosphorylation comparable to changes detected on western blot of parallel whole cell extracts (see in WINGMEN\_DataDefinitions&Tables Figure 1)

Similarly, the planned blood sample collection will provide sufficient serum and sodium heparin plasma to repeat assays for IGF bioactivity and metabolomic profiling if there are technical issues with initial assays. Both assays on circulating biomarkers will use controls in the form of recombinant IGF-1 and metabolite controls respectively. The lower detection limit for phospho-IGF-1R ELISA is 2 nmol/l IGF-1 equivalents, with approximately linear detection up to 20 nmol/l (WINGMEN\_DataDefinitions&Tables Figure 3).

#### 6.4 Pre-specified Subgroup Analysis

*Describe any pre-specified subgroups for analysis, together with the justification for their relevance and importance, which outcomes they will be analysed for (it may just be the primary outcome), and include methods of analysis (reporting is dealt with in the SAP – Data Definitions and Tables document). It is recommended that subgroup-treatment interaction methods are used with presentation using forest plots. Subgroups are usually pre-specified in the protocol, but additional subgroup analyses may be added to the SAP prior to the final data lock following the blinded analysis or publication of other trials/research. Clearly specify if this analysis will be descriptive or if statistical testing will be undertaken.*

Subgroup analysis will be performed to assess correlation of specific phenotypes/genotypes with response to IGF axis blockade, as described in WINGMEN\_DataDefinitions&Tables Section 5.3.1.

#### 6.5 Supplementary/ Additional Analyses and Outcomes

*Describe any supplementary/additional statistical analyses for primary or secondary outcomes required (if not already detailed elsewhere), e.g. complier-average causal effect analysis.*

*Describe any outcomes and analyses pre-specified as exploratory in the protocol. Include detailed definition and analysis methodology or if not being undertaken by the statistician clearly state this and signpost to separate documents where these are detailed together with who will perform these*

There will be no supplementary analyses of primary or secondary endpoints. The exploratory research/tertiary endpoints will be subject to detailed analysis as described in Section 4 above and WINGMEN\_DataDefinitions&Tables Section 5.

#### 6.6 Harms

*Provide sufficient detail on summarising safety data, e.g. information on severity, expectedness, and causality; details of how adverse events are coded or categorised; how adverse event data will be analysed, e.g. incident case analysis, intervention emergent analysis. Will adverse events/complications also be recorded, summarised and analysed – full details for reporting should be specified in the SAP – Data Definitions and Tables document.*

Potential harms include potential for drug toxicity and delay to standard of care surgery. Both will be captured as secondary endpoints and will be defined as described in WINGMEN\_DataDefinitions&Tables Section 2.2 and Table 2.

There is a risk of COVID-19 exposure and infection from trial-specific hospital attendances, but measures have been put in place to minimise this risk as far as possible. The WINGMEN recruitment site, Churchill Hospital, is

nominally COVID-19 free, and infected or potentially infected patients are treated at a geographically distinct site (John Radcliffe Hospital). The following procedures have also been put in place on site:

- All patients (in and outpatients) are screened upon entry to the Churchill site.
- Human traffic at the Churchill site is minimal, with face to face appointments avoided and staff working from home whenever possible.
- Face masks/social distancing/level 1 PPE for patient examinations and other protective measures are mandatory for staff at the Churchill site

Furthermore, this trial requires only 5 extra patients visits: screening and 4 treatment visits (unless surgery is unexpectedly delayed). The post-treatment End-of-Study trial assessment will be held on the same day as the routine 6-week post-operative assessment, and so will not involve an extra hospital visit. There is no evidence that treatment with an IGF inhibitory drug will cause patients to be immunosuppressed. Indeed, given experimental evidence that IGFs themselves can suppress the immune system [19, 20, 21], it is possible that treatment with xentuzumab could enhance immune responses. Therefore, we accept that extra hospital visits may confer additional COVID-19 risk, but the treatment itself should not increase this risk. There is no contraindication to having a COVID-19 vaccination before, during or after the study, and participants will be encouraged to do so if not already fully vaccinated.

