Treatment Duration	3.5-4 weeks (may be 3-10 weeks if standard of care surgery is early/delayed unexpectedly)	
Follow-up duration	6 weeks from date of surgery	

End of study	Last Patient Last Visit
--------------	-------------------------

SUMMARY SCHEDULE OF EVENTS

[figure not shown]
	Initial approach	Consent and screen (day -7 to 0) ^b	Day 1	Day 8	Day 15	Day 22 ^c	Day 29 (participants with surgery delayed beyond day 29 only)	Day 36 (and subsequent weeks in participants with surgery delayed only) maximum 10 doses	Day before surgery (& Early withdrawal)	Surgery (day 24-42 unless surgery has been delayed)	End of study visit (6 weeks after surgery +/- 7 days)
Demographic details		X									
Patient Information sheet	X										
Consent		X									
Medical history		X									
Concomitant medications		X	X	X	X	X ^c	X	X	X		X
Symptoms/Adverse events		X	X	X	X	X ^c	X	X	X		X
Height		X									
Weight		X			X				X		
Physical examination		X	X		X				X		X
ECOG performance status		X			X				X		X
Vital signs (pulse, BP, temperature)		X	X	X	X	X ^c	X	X	X		X
Haematology & biochemistry ^a		X	X ^b	X	X	X	X	X	X		X
Blood PSA, insulin, HbA1c, IGF-1		X	X ^b		X				X		X
ECG		X			X				X		
Retrieval of surplus tissue from diagnostic biopsy for research			X								
Research blood sample(s)				X					X	X	
Xentuzumab infusion			X	X	X	X ^c	X	X			
Radical prostatectomy with tissue collection										X	

^a **Haematology:** Hb, white blood cells (WBC) with differential count (neutrophils and lymphocytes) and platelets **Biochemistry:** sodium, potassium, calcium, phosphate, urea, creatinine, total protein, albumin, bilirubin, alkaline phosphatase (alk phos), AST and ALT, LDH and glucose. Patients will have had appropriate standard of care imaging assessments, usually MRI staging, and prostate biopsy, prior to being considered for the trial nb. The red X correspond to research activities

^b Same day visit results are not required before treatment

^c Visit not required if only 3 treatments are to be given

Study Flow Chart

Abbreviations

ADR	Adverse drug reaction
AE	Adverse Event
AESI	Adverse events of special interest
AKT	Protein Kinase B
ANC	Absolute Neutrophil Count
ALT	Alanine Transaminase
AR	Androgen receptor
AST	Aspartate Transaminase
BCT	Blood collection tubes
BrCa	Breast Cancer
CD4	Immune marker
CD8	Immune marker
CDK 4/6	Immune marker
CI	Chief Investigator
CRF	Case Report form
CRPC	Castrate Resistant Prostate Cancer
CTC	Circulating tumour cells

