16.1 Source Data

Source documents are where data are first recorded, and from which participants' CRF data are obtained. These include, but are not limited to, hospital records which could be electronic or paper (from which medical history and previous and concurrent medication may be summarised into the CRF), clinical and office charts, laboratory and pharmacy records, diaries, microfiches, radiographs and correspondence.

Primary Objective	Endpoint	Data required	CRF data	Non-CRF	Source data	Source data location
Assess the amount of IGF pathway blockade induced by xentuzumab	Phospho-IGF-1R and phospho-AKT (or downstream target) immunohistochemistry	IHC Sample analysis Results	No	Yes	Central laboratory records/ data files/ meta data	Central Laboratory- Oxford University
Secondary Objectives	Endpoints	Data required	CRF data ¹	Non-CRF ²	Source data	Source data location
Assess feasibility of treatment in the pre-prostatectomy setting	Number of patients whose radical prostatectomy is performed on schedule after 3 doses of xentuzumab.	Metrics from treatment data	Yes	No	Patient notes	Patient notes
Assess safety and tolerability of xentuzumab administered in the pre-prostatectomy setting	Treatment-related adverse events scored using CTCAE v5.0	Adverse events	Yes	No	Patient notes	Patient notes
Tertiary/ Exploratory Objectives	Endpoints	Data required	CRF data ¹	Non-CRF ²	Source data	Source data location
Assess change in PSA following administration of xentuzumab in the pre-prostatectomy setting	Change in serum PSA	Sample analysis results	No	Yes- Results from sample analysis	Central laboratory records/ data files/ meta data	Central Laboratory- Oxford University
Assess changes in tissue markers following administration of xentuzumab in the pre-prostatectomy setting	Changes by IHC and/or immunofluorescence on FFPE tissues in tissue markers e.g. Ki67 index, IGF-1R, RRM2, CD31, immune markers PD-L1, CD4, CD8, FoxP3.	IHC Results Multiplex immunofluorescence (mIF)	No	Yes- Results from IHC and mIF analysis	Central laboratory records/ data files/ meta data	Central Laboratory- Oxford University

Assess changes in circulating markers following administration of xentuzumab in the pre-prostatectomy setting	Changes in circulating markers of response to IGF blockade e.g. IGF-1, insulin, IGFBPs, serum IGF bioactivity, metabolomic profile, PBMC immunoprofiling	Sample analysis results	No	Yes	Central laboratory records/ data files/ meta data	Central Laboratory- Oxford University

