#### 4.1.2 Secondary endpoints

The feasibility of treatment in a pre-operative setting will be assessed as the number (percent) of patients whose radical prostatectomy was performed on schedule after 4 doses of xentuzumab. Any reasons for delay post-4 cycles will be tabulated.

The safety and tolerability of xentuzumab administered in the pre-prostatectomy setting will be examined through treatment-related adverse events scored using NCI-CTCAE v5.0. These results will be tabulated.

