## 6.1 Outcome Definitions

*Provide a simple list of all primary and secondary outcomes, together with time-points at which they are collected, with full details of definitions, and how these outcome variables will be generated and reported as provided in SAP - Data Definitions and Tables which should be cross-referenced.*

	Objectives	Endpoints
Primary endpoint	Assess the amount of IGF pathway inhibition induced by xentuzumab	Phospho-IGF-1R and phospho-S6 immunohistochemistry on tissue from biopsy and prostatectomy
Secondary endpoints	1. Feasibility of treatment in pre-operative setting 2. Assess safety and tolerability of xentuzumab administered in the pre-prostatectomy setting	1. Number of patients whose radical prostatectomy is performed within 7 days of the 4 th dose of xentuzumab (patients can receive up to 10 doses of xentuzumab if surgery is delayed) 2. Treatment-related adverse events scored using NCI-CTCAE v5.0
Tertiary/exploratory endpoints	1. Assess change in PSA following administration of xentuzumab in the pre-prostatectomy setting 2. Assess changes in tissue markers following administration of xentuzumab in the pre-prostatectomy setting 3. Assess changes in circulating markers following administration of xentuzumab in the pre-prostatectomy setting 4. Correlate changes in IGF-1R expression, IGF axis activity with cancer profile which may include mutation analysis, gene expression and phosphoproteomic profile	1. Change in serum PSA 2. Changes by IHC on FFPE tissues in tissue markers (e.g. Ki67 index, IGF-1R, RRM2, CD31, immune markers: PD-L1, CD4, CD8, FoxP3) 3. Changes in circulating markers of endocrine response to IGF blockade (e.g. IGF-1, insulin, IGFBPs, circulating IGF bioactivity, plasma metabolomic profile) 4. Tumour profiling (e.g. gene mutation panel, IHC for PTEN, FISH for TMPRSS2-ERG, transcriptional and phospho-proteomic profile of index tumour)

Table 3. Definition of WINGMEN outcomes.

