## 7 VALIDATION OF THE PRIMARY ANALYSIS

To validate the primary outcome and key secondary outcomes a statistician not involved in the trial will independently repeat the analyses detailed in this SAP using different statistical software (if possible). The results will be compared and any unresolved discrepancies will be reported in the Statistical Report (See OCTRU SOP STATS-005 Statistical Report). Primary and secondary outcomes are defined and tabulated in Section 6.1.

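### SAP Table 3 times feasibility from the fourth dose, so it does not measure the delay to scheduled surgery that SAP 6.6 says is captured

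*SAP*

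**What the plan says.** SAP 6.6 (Harms) says: "Potential harms include potential for drug toxicity and delay to standard of care surgery. Both will be captured as secondary endpoints". The same sentence then refers the definitions to the Data Definitions and Tables document (Section 2.2 and Table 2). The SAP Introduction calls that document integral to the plan, but it was not available for this review.

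Feasibility is the only secondary endpoint that concerns the timing of surgery. It is worded in three ways:

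- **SAP 6.1, Table 3:** "Number of patients whose radical prostatectomy is performed within 7 days of the" fourth dose. SAP 7 names this as the governing place: "Primary and secondary outcomes are defined and tabulated in Section 6.1".
- **SAP 4.1.2:** the number (percent) of "patients whose radical prostatectomy was performed on schedule after 4 doses of xentuzumab". Reasons for delay are tabulated, but only for delay after four cycles.
- **Protocol synopsis, Section 3 and Section 16.1:** surgery on schedule after 3 doses. Section 3 gives the time point as the date of surgery. Section 16.1 lists the data required as "Metrics from treatment data", with patient notes as the source.

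Neither document says what 'on schedule' is measured against. SAP 6.5 rules out supplementary analyses of secondary endpoints.

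**The concern.** Delay needs a reference date: when the operation was due. Table 3 uses the date of a dose instead. The two agree only if every man is booked for the week after his fourth dose and that dose is given on time.

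What is at stake is whether giving xentuzumab before surgery postpones a potentially curative operation. A rule timed from a dose can fail a man operated on exactly when booked. It can also pass a man whose operation slipped because of a drug reaction. If toxicity delays dosing as well as surgery, the starting point of the clock moves with the event it should detect.

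**Working it through.** The documents give no rate, threshold or sample size for feasibility, so there is no stated figure to reproduce. The check applies Table 3's rule to the protocol's own day numbers.

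**Inputs**
- Doses on days 1, 8, 15 and 22, so dose 4 is on day 22 (Protocol 7.3), with a visit window of ±1 day (Protocol 4.8).
- Surgery before day 22 after only 3 doses is accepted; a fifth dose is given on day 29 if surgery is later than that (Protocol 7.3).
- Missed doses are allowed if weekly dosing resumes and the last dose is within 6 days of surgery (Protocol 5.1 and 7.4).
- About 5 weeks (35 days) from informing the patient to surgery, with 2-3 days for discussion, consent and screening (Protocol 1.2).
- The protocol's surgery column: "Surgery (day 24-42 unless surgery has been delayed".

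**Rule.** Success if surgery day − dose 4 day ≤ 7. With dose 4 on day 22, the last success day is 22 + 7 = 29. With the visit window it is day 28 to day 30.

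**Operations on the booked date that count as failure**
1. If day 1 falls L days after the patient is informed, surgery falls on day 1 + 35 − L = 36 − L.
   - L = 3 gives day 33, which is 33 − 22 = 11 days after dose 4.
   - L = 2 gives day 34, which is 12 days after dose 4.
   - Both fail Table 3. Both men would have had a fifth dose on day 29, only 4 or 5 days before surgery, so they meet the 6-day evaluability limit.
   - Range: L from 2 to 6 gives days 34 to 30, all failures. Surgery reaches day 29 only when L is 7.
2. A man operated on as booked after 3 doses has no fourth dose to count from, so he cannot be a success.

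**Postponed operations that count as success**
1. Booked day 24, done day 28: 28 − 22 = 6 days after dose 4. This passes Table 3 and meets the 6-day limit, but the operation is 28 − 24 = 4 days late.
2. One missed weekly dose moves dose 4 to day 29 and the last success day to 29 + 7 = 36. That is 36 − 28 = 8 days late for a day-28 booking and 36 − 24 = 12 days late for a day-24 booking.
3. Two missed doses move dose 4 to day 36 and the last success day to day 43, which is 15 and 19 days late for the same bookings.

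**The protocol's use of 'delayed'.** In the Summary Schedule of Events, the surgery column treats days 24-42 as undelayed. The day 29 column of the same table is reserved for men whose surgery has been delayed past day 29. An operation on day 33 is therefore undelayed by one label and delayed by the other.

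**The case against.** The strongest reply is that SAP 6.6 does not rest on Table 3 alone. It sends the definition of delay to the Data Definitions document, which may use the booked date. This stands to the extent that nobody can say from the protocol and SAP that delay is defined nowhere. It does not rescue Table 3, which states an explicit rule in the section that SAP 7 names as defining the outcomes. If the companion document uses a booked date, the two conflict.

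Second, 'on schedule' most naturally means the scheduled date, and the patient notes are the listed source. SAP 4.1.2 also tabulates reasons for delay after four cycles, and a drug reaction would appear among the adverse events. So a slip from day 24 to day 28 would probably be described somewhere. That is fair, but the man would still be counted as a success. A delay that begins before the fourth dose falls outside that tabulation, and 'on schedule' remains undefined.

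Third, if surgery after day 29 is itself 'delayed', as the day 29 column implies, Table 3's cut-off agrees with the protocol. This is a real ambiguity. It does not fit the interval of about 5 weeks in Protocol 1.2, and it does nothing for the postponements counted as success.

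Finally, feasibility is descriptive, with no success threshold and no statistical analysis (SAP 6.2). That limits the consequence. It does not make the count answer the question put to it.

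**Conclusion.** The concern holds for Table 3 as written. It measures a dose-to-surgery interval, conflicts with 'on schedule' in SAP 4.1.2 and the protocol, and misclassifies in both directions on the protocol's own day numbers. Undelayed surgery near day 33-34 fails, assuming the stated interval of about 35 days and lead-in of 2-3 days. Postponements of 4 days, or of 8 to 12 days with one missed dose, can pass. How many men this affects cannot be stated, and drug-caused delay may be rare; this endpoint could not show that.

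Three stronger readings are tempting but not supported:

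- **That 68% of operations are misclassified.** Days 30-42 are 13 of the 19 days in the 24-42 window, and 13/19 = 68%. That is a share of calendar days. The distribution of booked dates is not given, and the protocol also calls surgery after day 29 delayed.
- **That the percentage is biased upward by its denominator.** SAP 6.2 lists as non-evaluable and replaceable "Patients who for any reason do not have their planned standard of care prostatectomy", along with men given fewer than 3 doses. That list concerns the primary endpoint, and SAP 4.2 places the analysis populations in the companion document. The denominator is unstated in the SAP, not shown to be wrong.
- **That delay goes wholly unrecorded.** Some reasons are tabulated, and the companion document may define delay.

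**What to change.** In SAP Table 3 and 4.1.2:

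1. Define 'on schedule' as an actual surgery date no later than the date booked at registration, taken from the patient notes.
2. Report days of delay (actual minus booked date), with the reason and relation to drug, for delay arising at any point in treatment.
3. State the denominator as all men who received at least one dose, including any replaced for the primary endpoint, with no surgery counted as not on schedule.
4. Report the dose-to-surgery interval separately, as a compliance measure.

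Check Section 2.2 and Table 2 of the Data Definitions document. If they define delay, bring Table 3 into line with them. Three conflicts must also be reconciled: the two uses of 'delayed' in the protocol's schedule, the 3-dose and 4-dose wordings of the endpoint, and the 7-day limit in Table 3 against the 6-day evaluability limit.

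The cost is SAP wording and one extra date per man. SAP 3.4.4 says recruitment is complete, so the date must be collected retrospectively; this assumes that the notes hold the original booking. The percentage may be less favourable, because treated men who had no surgery would count against it. No dose or clinical rule changes.
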